- (xvii). Uncontrolled cardiac angina or symptomatic congestive cardiac failure (NYHA Class III or IV).

7 RULES FOR CONCOMITANT IBD MEDICATIONS.

- (i). Subjects receiving oral 5-aminosalicylates or oral corticosteroids (prednisone ≤40mg per day or its equivalent) must receive stable doses for at least 2 weeks prior to commencement of the study.
- (ii). Subjects receiving azathioprine, 6-mercaptopurine, methotrexate, cyclosporine, tacrolimus, sirolimus or mycophenolate mofetil must receive stable doses for at least 4 weeks prior to commencement of the study.
- (iii). Subjects receiving concurrent tacrolimus and sirolimus will be excluded, due to the increased risk of renal failure seen in previous studies when these medications were co-prescribed.
- (iv). Rectally administered steroids or mesalamine will be discontinued 2 weeks before screening.
- (v). Subjects receiving IV steroids or biologic agents must undergo a 4-week wash-out period prior to enrolment.

8 SUBJECT ENTRY.

8.1 Recruitment and Accrual.

Subjects enrolled in the trial will be identified through the gastroenterology department at Boston Children's Hospital.

8.2 Study Site Responsible Investigator.

Boston Children's Hospital

[name] MD PhD

Boston Children's Hospital

Division of Medicine (GI/Nutrition),

[name],

[name].

[contact]

9 TREATMENT PROGRAM.

9.1 Description of Study Design.

This is an open-label phase Ib/IIa clinical trial to determine the safety and maximum tolerated dose of daily SC IL-2 in eligible subjects with moderate to severe ulcerative colitis (UC). Subject cohorts will receive escalating dose levels of IL-2, as shown in Table 1 (page 22). A minimum of three subjects will be treated in each cohort, with an additional ten subjects treated at the presumptive MTD.

9.2 Dose Cohorts.

[figure not shown]
Koreth *et al.*⁵¹ treated subjects with steroid-resistant GvHD with doses ranging from 0.3-3.0x10⁶ IU/m²/day. Doses of 0.3 and 1.0x10⁶ IU/m²/day were well-tolerated. 1.0x10⁶ IU/m²/day was found to be the MTD in this study. Dose limiting toxicity (DLT) occurred at 3.0x10⁶ IU/m²/day. Saadoun *et al.*⁵² treated subjects with treatment-resistant HCV-associated vasculitis at a dose of 1.5x10⁶ IU/day, which was well-tolerated in this study. The side-effects seen in these studies are detailed in Section 4.6 (page 13).

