Dose level A: 0.3x10⁶ IU/m²/day. Koreth *et al.*⁵¹ found that a dose of 0.3x10⁶ IU/m²/day was well tolerated in a cohort of subjects with steroid-resistant GvHD. Consequently, we propose to commence treatment at this dose.

Dose level B: 1x10⁶ IU/m²/day. Provided dose level A is tolerated, the dose will then be escalated to dose level B. This was the MTD in the Koreth *et al.* study⁵¹.

Dose level C: 1.5x10⁶ IU/m²/day. Intolerable constitutional symptoms occurred at the highest dose in the Koreth *et al.* study⁵¹ (3x10⁶ IU/m²/day). Consequently, we propose that the highest dose in this study will be 1.5x10⁶ IU/m²/day, or 50% of the dose at which intolerable constitutional symptoms occurred in that study. This dose has been included to maximize the potential for clinical response, while minimizing the potential for toxicity. This dose remains two orders of magnitude below those used in studies of IL-2 for metastatic melanoma and RCC⁴⁰.

Table 1: Dose Escalation Cohorts.

Cohort	IL-2 Dose ($\text{IU}/\text{m}^2/\text{day}$)	Projected n in each cohort
Dose Level A	0.3×10^6	3
Dose Level B	1×10^6	3
Dose Level C	1.5×10^6	$3 + 3 + 10^*$

*Assuming dose level C is shown to be the MTD.

Adapted from Koreth *et al.*⁵¹

9.3 Dose Escalation Schema.

There will be 3 dose levels, ranging from 0.3 to $1.5 \times 10^6 \text{ IU}/\text{m}^2/\text{day}$. Each subject will be treated at a single dose level. The first three subjects will be enrolled at the lowest dose level: dose level A. These subjects will be treated sequentially, so that none of these subjects will receive the study drug concurrently. The dose will be escalated as per the protocol below.

The maximum tolerated dose (MTD) is the highest tolerated dose level at which a minimum of 6 subjects have been evaluated, with fewer than 2 evaluable subjects in 6 experiencing a dose limiting toxicity (DLT); i.e. DLT in $\leq 1/6$ evaluable subjects.

A dose escalation schema has been designed in order to identify the MTD.

9.3.1 Dose Level A.

Three evaluable subjects will be recruited at dose level A. They will be monitored for the development of DLT during their 8-week treatment course.

If none (0/3) of these subjects experience a DLT during the 8-week treatment, dose escalation will occur so that the next three subjects will be enrolled at dose level B.

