If one of the first three subjects treated (1/3) at dose level A experiences a DLT during the 8-week treatment, an additional 3 subjects will be enrolled at dose level A. Up to six subjects in total will then complete treatment at dose level A. If no further DLTs occur in this group of 6 subjects (i.e. 1/6 subjects with DLT), dose escalation will occur so that the next three subjects will be enrolled at dose level B. If DLTs occur in two subjects in this group (i.e. 2/6 subjects with DLT), then dose level A has not been tolerated and the study will be terminated early.

If two of the first three subjects treated (2/3) at dose level A experience DLT during the 8-week treatment, then dose level A has not been tolerated and the study will be terminated early.

The dose may be reduced from dose level B to dose level A. If this occurs and six subjects have already been treated at dose level A, then dose level A is the MTD. If this occurs and only three subjects have been treated at dose level A, then a further three subjects will be recruited at dose level A. If 0 or 1 subject in this group of 6 experience a DLT, then dose level A will be the MTD. If 2 subjects in this group of 6 experience a DLT, then the study will be terminated early.

9.3.2 Dose Level B.

After successful dose escalation from dose level A, the next three evaluable subjects will be treated at dose level B. They will be monitored for the development of DLT during their 8-week treatment course.

If none (0/3) of these subjects experience a DLT during the 8-week treatment, dose escalation will occur so that the next three subjects will be enrolled at dose level C.

If one of the first three subjects treated at dose level B (1/3) experiences a DLT during the 8-week treatment, an additional 3 subjects will be enrolled at dose level B. Up to six subjects in total will then complete treatment at dose level B. If no further DLTs occur in this group of 6 subjects (i.e. 1/6 subjects with DLT), dose escalation will occur so that the next three subjects will be enrolled at dose level C. If DLTs occur in two subjects in this group (i.e. 2/6 subjects with DLT), then dose level B has not been tolerated and the dose will be reduced to dose level A (see Section 9.3.1, page 22).

If two (2/3) of these subjects experience a DLT during the 8-week treatment, then dose level B has not been tolerated and the dose will be reduced to dose level A (see Section 9.3.1, page 22).

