The dose may be reduced from dose level C to dose level B. If this occurs and six subjects have already been treated at dose level B, then dose level B is the MTD. If this occurs and only three subjects have been treated at dose level B, then a further three subjects will be recruited at dose level B. If 0 or 1 subject in this group of 6 experience a DLT, then dose level B will be the MTD. If 2 subjects in this group of 6 experience a DLT, then the dose will be reduced from dose level B to dose level A.

9.3.3 Dose Level C.

After successful dose escalation from dose level B, the next three evaluable subjects will be treated at dose level C. They will be monitored for the development of DLT during their 8-week treatment course.

If none or one (0-1/3) of the first three subjects recruited at dose level C experience a DLT during the 8-week treatment, a further three subjects will be recruited at this dose level. Up to six subjects in total will then complete treatment at dose level C. If no further DLTs occur in this group of 6 subjects (i.e. 0-1/6 subjects with DLT), dose level C will be the MTD. If DLTs occur in two subjects in this group (i.e. 2/6 subjects with DLT), then dose level C has not been tolerated and the dose will be reduced to dose level B (see Section 9.3.2, page 23).

If two of the first three subjects treated at dose level C (2/3) experience a DLT during the 8-week treatment, then dose level C has not been tolerated and the dose will be reduced to dose level B (see Section 9.3.2, page 23).

The dose escalation schema is summarized in Table 2 (page 25).

9.3.4 Recruitment of Additional Subjects.

An additional 10 subjects will be treated at the MTD to further characterize the safety and efficacy of the study drug per the definition of MTD above.

Table 2: Rules for Dose Escalation and Allowable DLTs Per Cohort

# DLT per cohort	Dose escalation rule
0/3	
Accrue the next 3 subjects at next dose levelIf dose level C, accrue 3 additional subjects at this level
1/3	
Accrue 3 additional subjects at current dose level

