2/3	
Current dose level has not been tolerated. Reduce dose to the lower dose level
If only 3 subjects have been treated at the lower dose level, accrue an additional 3 subjects at the lower dose level.If 6 subjects have already been treated at the lower dose level, the lower dose level is the MTD.If this occurs at dose level A, the study will be terminated early.
1/3 + 0/3 (1/6)	
Escalate dose. Accrue 3 new subjects at next highest dose level. If 0/6 or 1/6 DLTs at dose level C, then this is the MTD.
1/3 + 1/3 (2/6)	
Current dose level has not been tolerated. Reduce the dose. If this occurs at the lowest dose level, the study will be terminated early.

To be read with reference to Section 9.3 (page 22), above. Adapted from Koreth *et al.*⁵¹

9.4 Determination of Maximum Tolerated Dose.

The maximum tolerated dose (MTD) is the highest tolerated dose level at which a minimum of 6 subjects have been evaluated, with fewer than 2 evaluable subjects in 6 experiencing a dose limiting toxicity (DLT); i.e. DLT in $\leq 1/6$ evaluable subjects. **In addition to the above, at least 1 patient should meet the criteria for response or remission for it to be considered the MTD.**

Subjects will be considered unevaluable for DLT if they are removed from the study or die without developing DLT prior to receiving at least 8 weeks of IL-2 therapy. If there are fewer than 3 evaluable subjects in a cohort, additional subjects will be added at that dose level.

Intolerable lower grade toxicity that does not meet the definition of DLT, but still means that a subject is unable to complete the per-protocol treatment will be taken as equivalent to a DLT for the purpose of assessing dose escalation. If ≥ 2 subjects in a cohort of 3 refuse to continue at that dose level for at least 8 weeks due to intolerable lower grade toxicity, that dose level will not be regarded as the MTD.

9.5 Definition of Dose Limiting Toxicities.

Organ toxicities will be assessed at scheduled clinical visits and graded according to the National Cancer Institute Common Terminology Criteria for Adverse Events v4.0⁵⁴.

- (i). **Anaphylaxis:** Life threatening anaphylaxis due to the study drug is considered a DLT.
- (ii). **Grade 4 toxicity:** Grade 4 toxicity (except colitis, see below) directly related to IL-2 by week ~~11~~8 of IL-2 treatment is considered a DLT.

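### A tolerated dose with no responder is the MTD under 9.3 and Table 2 but not under 9.4, and the plan does not settle the outcome

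*Combined protocol and SAP*

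**What the plan says.** Section 15 names determination of the MTD as the primary endpoint.

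Section 9.3 defines it by tolerability only: "The maximum tolerated dose (MTD) is the highest tolerated dose level at which a minimum of 6 subjects have been evaluated", with DLT in at most 1 of 6. The dose-level rules apply that definition with no other condition:

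- 9.3.1, after a reduction to level A: "If 0 or 1 subject in this group of 6 experience a DLT, then dose level A will be the MTD".
- 9.3.2, after a reduction to level B: "If 0 or 1 subject in this group of 6 experience a DLT, then dose level B will be the MTD".
- 9.3.3, level C: "i.e. 0-1/6 subjects with DLT), dose level C will be the MTD".
- Table 2, level C: "If 0/6 or 1/6 DLTs at dose level C, then this is the MTD".

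Section 9.4 repeats the 9.3 definition and then adds, in bold, that "at least 1 patient should meet the criteria for response or remission for it to be considered the MTD". This condition appears nowhere else. Section 14.2 refers the reader to Section 9 as a whole for how the MTD is determined.

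Ten further subjects are then treated. Section 9.1 describes this as "with an additional ten subjects treated at the presumptive MTD". Section 9.3.4 has the 10 treated at the MTD, 15.1 has them treated after the MTD is established, and the footnote to Table 1 carries the condition "Assuming dose level C is shown to be the MTD".

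**The concern.** If dose level C has 0 or 1 DLT in 6 subjects and nobody meets response or remission, 9.3.3 and Table 2 name it as the MTD and 9.4 says that it is not. Someone who follows the plan exactly reaches two different answers on the primary endpoint. The same clash can arise at B or A after a reduction.

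The 10-subject expansion is also at stake, and 15.1 bases the toxicity-rate estimate on those 10 subjects. If the responder condition is judged on the first 6 and fails, the plan does not say whether the expansion opens.

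Timing makes this more serious. DLT observation and the Mayo assessment are both complete at week 8, the trial is open-label, and the Mayo score includes a physician's global assessment. Without a written rule, the choice of which subjects count, and of what follows when none responds, would be made with the outcomes in view.

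**Working it through.** **1. The plan's own figures.** Table 6 follows from the standard 3+3 rule, where escalation needs 0/3, or 1/3 followed by 0/3:

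P(escalate) = (1-p)^3 + 3p(1-p)^2 × (1-p)^3.

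For p = 10/20/30/40/50/60% this gives 0.906/0.709/0.494/0.309/0.172/0.082, which matches every row. Response does not enter escalation, so Table 6 is right and the condition in 9.4 does not disturb it.

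**2. The rules side by side, for 0-1/6 DLTs at level C.**

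| Responders | 9.3, 9.3.3, Table 2 | 9.4 |
|---|---|---|
| At least 1 | MTD | MTD |
| None | MTD | Not the MTD |

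Every stated action (escalate, add 3, reduce, terminate) is triggered by DLTs, or by toxicity treated as a DLT. None is triggered by absence of response.

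**3. Which subjects count.** The dose has 6 subjects before expansion and 6 + 10 = 16 after it. Section 9.3.4, 15.1 and the Table 1 footnote place the MTD before the 10 are treated, which implies the first 6. The word *presumptive* in 9.1 allows the MTD to be confirmed afterwards, on 16.

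**4. Chance of no responder.** The documents give no response rate r for IL-2 in UC, so r is assumed, with subjects taken as independent. P(none in n) = (1-r)^n.

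| Assumed r | None in 6 | None in 16 | Readings differ |
|---|---|---|---|
| 10% | 0.531 | 0.185 | 0.346 |
| 20% | 0.262 | 0.028 | 0.234 |
| 30% | 0.118 | 0.003 | 0.114 |
| 40% | 0.047 | 0.0003 | 0.046 |

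The last column is the difference of the two before it: no responder in the first 6 but at least one among the next 10.

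These figures are conditional on the dose being tolerated. At level C, P(0-1/6 DLT) = (1-p)^6 + 6p(1-p)^5 = 0.886/0.655/0.420 at assumed DLT rates p of 10/20/30%. At p = 20%, with response independent of DLT, the chance that C is tolerated with no responder in 6 is 0.655 times the second column: 0.348/0.172/0.077/0.031.

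**5. Whether a lower level can qualify instead.** On a cumulative reading, a lower level qualifies only if it already has 6 subjects, at most 1 DLT and a responder. On the projected path in Table 1, A and B have 3 subjects each and cannot. Among escalations from a level, the share with 6 treated is 3p(1-p)^5 / [(1-p)^3 + 3p(1-p)^5]:

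- p = 10%: 0.177/0.906 = 0.195
- p = 20%: 0.197/0.709 = 0.277

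With the same p at A and B, the chance that at least one of them has 6 when C is reached is 1 - (1 - 0.195)^2 = 35%, or 1 - (1 - 0.277)^2 = 48%. That level also needs a responder.

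**The case against.** The strongest reply is that 9.4 is written as an addition to the DLT rule, that 14.2 covers all of Section 9, and that the sections should therefore be read together. On that reading 9.4 does state a consequence: without a responder the dose is not the MTD. Ending without an MTD is also not foreign to the plan, because 9.3.1 terminates the study if level A is not tolerated. Section 13 gives the DSMB authority over stopping points and over continuation, modification or termination.

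Most of this stands. A reader might infer that the plan has no answer at all and that the trial would stall. The documents do not support that: there is an implied outcome, a named decision-maker, and in some paths a lower level that qualifies. What is left is that 9.3.3 and Table 2 as written still name that dose the MTD, and that DSMB discretion is not a pre-set rule for the expansion or for reporting. If the verb in 9.4 is taken as advisory, it is unclear whether the condition binds at all.

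A reader might also infer that the plan is silent on the denominator. It is not: three places lean towards the first 6, and only 9.1 clearly points the other way. This is an inconsistency in wording rather than a blank.

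Finally, the size depends on r. The 69% response quoted in Section 4.1 is for infliximab and does not set r for IL-2, but nothing in the documents supports a low rate either. At 40% or above the problem is rare.

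**Conclusion.** The plan is wrong as written on this point and should be fixed. For a tolerated dose with no responder, following 9.3.3 and Table 2 gives a different primary result from following 9.4. The cumulative reading resolves whether the dose is the MTD, but not whether the expansion opens or what is reported.

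At assumed response rates of 10-30%, the chance of no responder is 53-12% if the first 6 count and 19-0.3% if all 16 count. At 40% it is 5% and below 0.1%. These rest on an assumed r, on independence between subjects and, for the joint figures, on independence of response and DLT. They are chances of seeing no responder. It would be tempting to read them as the chance that the trial ends unresolved, but they ignore lower levels that may already qualify.

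A reader might go further and conclude that the dose-escalation properties or subject safety are compromised. They are not: escalation, Table 6 and the safety rules do not depend on the responder condition. Nor do the documents show that a responder condition has no place in the MTD. The sponsor added it deliberately, and keeping it is defensible once the rule is complete.

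**What to change.** In 9.3, 9.3.1 to 9.3.3, 9.3.4, Table 2 and 15.1, call the level with 0-1/6 DLTs the presumptive MTD, the term already used in 9.1, and let it open the 10-subject expansion. The Table 1 footnote should follow. In 9.4, state that:

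- the responder condition is judged once, on the week 8 assessment, among all 16 subjects at that dose;
- if none responds, the dose is reported as the highest tolerated dose without observed activity and no MTD is declared;
- there is no step-down.

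This changes wording only. It adds no subjects, visits or assessments, and the maximum in 15.2 stays at 6 + 6 + 6 + 10 = 28.

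It has three costs. The primary endpoint may end without a declared MTD. The expansion may run at a dose with no responder in the first 6. It also closes the route by which a lower level that already has 6 subjects and a responder could qualify.

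An acceptable alternative is a DLT-only MTD throughout, with response reported separately. A dose with no responder would then still be called the MTD. That choice belongs to the sponsor.

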- (iii). **Grade 3 toxicity:** IL-2 will be withheld for grade 3 toxicity (except colitis).
- (iv). **Development of a life-threatening infection:** Development of a life threatening infection, as assessed by the treating physician, prior to week 8 of IL-2 therapy will be considered a DLT. IL-2 will be withheld.
- (v). **Grade 2 renal toxicity:** IL-2 will be withheld in the event of a grade 2 renal toxicity (creatinine = 1.5-3.0 x ULN).

Development of toxic megacolon or colitis requiring immediate surgical intervention is a well-described risk of active UC. Consequently, it will not be considered a DLT. However, IL-2 will be discontinued.

9.6 Clinical Assessments for Toxicity.

Subjects will undergo regular clinical examination (history and physical examination), blood tests and other tests as indicated at scheduled visits in order to detect potential drug toxicity, as detailed in Section 11 (Page 31).

9.7 Extended Treatment with Low-Dose IL-2.

After completing 8 weeks of IL-2 therapy, subjects who have achieved a clinical response or entered remission (see Section 14, Page 43, for definitions) at any dose level and have an acceptable toxicity profile will be allowed to continue treatment at that dose level, at the discretion of the treating physician. These subjects will be seen in clinic every 3 months for a year, after which they will be followed by the referring gastroenterologist. Prometheus Laboratories will continue to supply IL-2 for up to one year after completing 8 weeks of IL-2 therapy to subjects who have achieved a clinical response or entered remission at any dose level and have an acceptable toxicity profile.

Subjects on extended duration IL-2 therapy will not be evaluable for toxicity and DLT endpoints. The addition of other medications (except the combination of sirolimus and tacrolimus) will be permitted at the discretion of the treating physician. Subject assessment while on extended treatment with IL-2 is detailed in Section 11.4 (page 34). In the event of toxicity attributable to IL-2, therapy will be discontinued.

10 STUDY DRUG: ALDESLEUKIN.

10.1 Formulation, Reconstitution and Storage.

Recombinant human IL-2 (aldesleukin, Proleukin®) is supplied free of charge by Prometheus Laboratories, Inc. (San Diego, CA).

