Soiffer et al. ⁵⁰	0.2-0.6x10 ⁶ IU/m ² /day	Enhance graft vs. leukemia effect following HSCT	29	Fatigue	15 (52)
				Temp >38°C	14 (48)
				Nausea/vomiting	11 (38)
				Myalgia	9 (31)
				Rash	9 (31)
				Diarrhea	7 (24)
				Edema	6 (21)
				Dyspnea	6 (21)
				Catheter infection	5 (17)
				Thyroid dysfunction	2 (7)
Koreth et al. ⁵¹	0.3-3x10 ⁶ IU/m ² /day	Treatment of steroid-resistant GvHD	28	Thrombocytopenia	2 (7)
				Injection site induration	3 (11)
				Infections*	3 (11)
				Renal failure**	2 (7)
				Renal dysfunction	1 (4)
				Flu-like symptoms	1 (4)
				Thrombocytopenia	1 (4)
Saadoun et al. ⁵²	1.5-3x10 ⁶ IU/day	Treatment of HCV-associated vasculitis	10	Fatigue	4 (40)
				Flu-like symptoms	4 (40)
				Injection site induration	2 (20)
				Arterial hypertension	1 (10)
				Myalgia	1 (10)

* Recurrent MRSA pneumonia (1), *Hemophilus influenzae* type-B bacteremia (1), MRSA furuncle (1)

** Thrombotic microangiopathic renal failure in two subjects taking tacrolimus and sirolimus. This is a recognized complication of this combination of medications.

11.8 Criteria for Treatment Discontinuation.

Subjects will be removed from the study and therapy with IL-2 should be abandoned for any of the following circumstances if they are deemed possibly, probably or definitely related to IL-2, or per subject preference:

- The subject withdraws his/her consent at any time.
- Anaphylactic reaction to IL-2.
- Life threatening infection on IL-2.
- Other grade 4 toxic event.
- Grade 3 toxicity.
- Grade 2 renal toxicity.
- The development of toxic megacolon or colitis requiring immediate surgical intervention.
- At the discretion of the treating physician.

11.9 Dose Modification/Toxicity Management.

In the event of IL-2 related toxicity that does not meet the requirement for treatment discontinuation (grade 2 toxicity or less, excluding grade 2 renal toxicity), the treating physician may elect to withhold IL-2 to allow the toxicity to resolve. IL-2 can be recommenced at 50% of the target dose if the toxicity resolves to grade 1 or better within 2 weeks. At the discretion of the treating physician, if re-introduction of IL-2 is tolerated by the subject, the dose of can be escalated to the target dose.

12 REPORTING OF UNANTICIPATED PROBLEMS INVOLVING RISKS TO RESEARCH SUBJECTS, INCLUDING ADVERSE EVENTS.

12.1 Reporting to the Principal Investigator.

The following events will be reported to the principal investigator within 24 hours of being known:

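### A grade 4 event judged only possibly related to IL-2 takes the subject off treatment (11.8) but, as 9.4 and 9.5(ii) are worded, is left out of the DLT count that sets the MTD

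*Combined protocol and SAP*

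**What the plan says.** Three rules of the combined protocol and SAP have to be read together.

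- **What counts (9.5(ii)).** A grade 4 event is a DLT under this wording: "Grade 4 toxicity (except colitis, see below) directly related to IL-2 by week" 8. The attribution term is not defined anywhere in the document.
- **What ends treatment (11.8).** Subjects come off IL-2 for the listed events "if they are deemed possibly, probably or definitely related to IL-2". The list includes "Other grade 4 toxic event", grade 3 toxicity and grade 2 renal toxicity.
- **Who is evaluable (9.4).** "Subjects will be considered unevaluable for DLT if they are removed from the study or die without developing DLT" before they have received 8 weeks of IL-2. A cohort left with fewer than three evaluable subjects is topped up.

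Section 9.4 adds a rescue sentence. Intolerable lower grade toxicity that falls short of a DLT but prevents completion "will be taken as equivalent to a DLT for the purpose of assessing dose escalation".

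Two kinds of life-threatening event lie outside the problem. Anaphylaxis due to the drug is a DLT under 9.5(i). Infection is a DLT under 9.5(iv) with no attribution test: "Development of a life threatening infection, as assessed by the treating physician". Colitis is excluded on purpose.

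For the remaining two entries in 9.5, the text gives an action but no DLT status. Item (iii) reads "IL-2 will be withheld for grade 3 toxicity (except colitis"), and item (v) says the same of grade 2 renal toxicity.

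**The concern.** The MTD is the stated primary endpoint (section 15). It is set by whether 0, 1 or 2 DLTs occur among three to six evaluable subjects, so one reclassified subject can change the decision.

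Removal and counting use different attribution tests. A grade 4 event that the physician thinks IL-2 may have caused is serious enough to abandon the drug. If it is judged only possibly related, it does not naturally meet the 9.5(ii) test. The rescue sentence in 9.4 speaks of lower grade toxicity, so it does not plainly reach a grade 4 event. The subject then becomes unevaluable and the event never enters the count.

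A secondary point is that 9.5 does not say whether a grade 3 or grade 2 renal removal is a DLT, a DLT-equivalent or an unevaluable case.

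**Working it through.** **Step 1: reproduce Table 6.** For the 3+3 rule in 9.3 (escalate on 0/3, or on 1/3 followed by 0/3), with p the DLT rate per evaluable subject and q = 1 − p:

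P(escalate) = q³ + 3pq² × q³

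At p = 0.10 this is 0.729 + 0.243 × 0.729 = 0.906. At 10% to 60% it gives 0.906, 0.709, 0.494, 0.309, 0.172 and 0.082. Table 6 has 0.91, 0.71, 0.49, 0.31, 0.17 and 0.08, so the plan's figures are right. The question is which events p refers to.

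**Step 2: follow the rules through one case.** At dose level B, suppose two of the first three subjects have a grade 4 event (not infection, anaphylaxis or colitis) judged possibly related.

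- As written: both are removed (11.8), neither has a DLT (9.5(ii)), and both are unevaluable (9.4). One evaluable subject remains and two are added. If all three evaluable subjects are free of DLT, the level scores 0/3 and the dose goes up to C.
- If the events count: the level scores 2/3 and the dose goes down to A (9.3.2).

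**Step 3: size of the effect.** The inputs below are assumptions, because the documents give no rate for these events in UC.

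- d = probability of a counted DLT = 0.10.
- g = probability of removal for an event that is not counted = 0.02, 0.05 or 0.10. The two outcomes are taken as exclusive within a subject.
- As written (removed and replaced): p = d / (1 − g).
- If counted: p = d + g.

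| g | p as written | P(escalate) as written | p if counted | P(escalate) if counted |
|---|---|---|---|---|
| 0.02 | 0.102 | 0.90 | 0.12 | 0.87 |
| 0.05 | 0.105 | 0.90 | 0.15 | 0.81 |
| 0.10 | 0.111 | 0.89 | 0.20 | 0.71 |

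For g = 0.10 as written: q = 0.889, q³ = 0.702, 3pq² = 0.263, and 0.702 + 0.263 × 0.702 = 0.887. If counted: 0.512 + 0.384 × 0.512 = 0.709.

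**Step 4: sensitivity.**

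- If half of the uncounted removals are in practice captured, p = (d + g/2)/(1 − g/2). P(escalate) is then 0.89, 0.86 and 0.80.
- With d = 0.05, as written against counted: 0.97 v 0.95, 0.97 v 0.91, and 0.97 v 0.81.
- If g = 0 there is no effect.

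**Step 5: where the shift comes from.** If the removed subject stayed in the denominator as a non-DLT, p would be 0.10 and P(escalate) 0.906. Replacement gives 0.887 at g = 0.10, which is slightly lower. The understatement therefore comes from not counting the event, not from replacing the subject.

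**Step 6: how often it could arise.** The chance of at least one such event in three subjects is 1 − (1 − g)³ = 6%, 14% and 27%. The chance of two or more in three, as in Step 2, is 3g²(1 − g) + g³ = 0.1%, 0.7% and 2.8%.

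**The case against.** Stopping a drug on suspicion while counting only firmer attribution is a recognisable design choice, and 9.5 closes by separating drug toxicity from complications of UC. The undefined term might therefore mean no more than due to the drug rather than the disease. That is possible, but the protocol does not say so, and an event judged only possibly related would still be in doubt. The point stands for that category. A reader might infer that probably related events are excluded too. The text does not support that firmly, because the undefined term could well cover them.

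The case in Step 2 is rare at the assumed rates. The DSMB reviews every serious adverse event and DLT, and section 13 gives it power to set stopping points for subjects and for the study. That softens the safety consequence, but it does not change the count that defines the MTD.

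A reader might also infer that grade 3 and grade 2 renal removals go uncounted. Section 9.4 probably captures most of them: a subject removed under 11.8 cannot complete treatment, and the rescue sentence carries no strict attribution test. What remains open is the word intolerable, chiefly for a creatinine rise without symptoms.

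Two further readings fail.

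- It might seem that the equivalence sentence lapses at level C, where no higher dose exists, leaving only the sentence on subjects who "refuse to continue at that dose level for at least 8 weeks due to intolerable lower grade toxicity". But 9.3, 14.2 and Table 2 treat the MTD decision as part of the dose escalation scheme, including at level C.
- It might seem that early toxicity removals vanish from the 10-subject expansion estimate in 15.1. That section speaks of a toxicity rate, whereas 9.4 defines evaluability for DLT. Side-effects are assessed at every visit (14.1), and enrolment and completion numbers are reported (14.3). Silence on the denominator is not exclusion.

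**Conclusion.** The conflict between 9.4, 9.5(ii) and 11.8 is in the current text, and no other section resolves it. It is clear for a grade 4 event judged only possibly related to IL-2, other than infection, anaphylaxis or colitis. Leaving such an event out of the count favours escalation. The unstated DLT status of grade 3 and grade 2 renal removals is a lesser ambiguity.

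The size is uncertain. At an assumed 10% counted DLT rate, the probability of escalation is overstated by about 3 points at 2% uncounted removals, 8 points at 5% and 18 points at 10%, compared with counting them. It is nil if all removals are captured. The 1/28 grade 2 renal rate quoted in 4.6 should not be used as the size of the grade 4 gap, because it describes a different event.

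This should be fixed: it affects the rule for the primary endpoint, and the repair is cheap.

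**What to change.** 1. In 9.5(ii), replace the undefined attribution term with the 11.8 standard (possibly, probably or definitely related), and keep the colitis exception.
2. In 9.4, state that a subject removed under 11.8 before 8 weeks for grade 3 or grade 2 renal toxicity at least possibly related to IL-2 is a DLT-equivalent and is not treated as unevaluable. Except colitis of any grade and toxic megacolon, which stay outside the DLT count as 9.5 intends. Without that exception the new sentence would contradict 9.5.

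The cost is a text amendment with no new data collection. Table 6 stands, with its DLT rate now read under the wider definition. The second change also settles a design question that the protocol leaves open, so the investigators should agree to it knowingly.

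The downside is that a dose level may fail sooner, including on events that are in truth unrelated to IL-2. If every added event were unrelated, the fall in the probability of escalation (0.90 to 0.87 at 2%, 0.89 to 0.71 at 10%) would bring no safety gain.
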